- Comparison of National eye Institute (NEI) to Ocular Staining Score (OSS) (DEWS II recommendation) staining scheme for efficiency
- 2. Repeatability of the above two staining schemes and meibomian gland secretion scores

Pharmacokinetic measures

• The patients will have blood samples (20 ml) drawn for the determination of total serum testosterone. Blood will be drawn at baseline and within two hours of dose application at Week 4 visit.

Safety measures

- Adverse events (treatment related and treatment unrelated)
- Visual acuity (BCVA ETDRS)
- Biomicroscopy
- Ophthalmoscopy exam
- IOP
- Male scalp hair evaluation
- Female hair evaluation (upper lip, chin, cheeks, scalp)

Subjects

Subjects will consist of a convenience sample of patients over 18 years old with signs and symptoms of dry eye disease (DED). Moderate to severe dry eye subjects who have either aqueous tear deficiency or evaporative dry eye related to meibomian gland

dysfunction will be recruited. The diagnosis of DED is made according to the DEWS II diagnostic criteria based on:

- 1. DE symptomatology: OSDI score \geq 13 and Modified Schein score \geq 7.5
- 2. Plus one of the following:
 - a. NIBUT < 10 seconds or fluorescein breakup time ≤ 6.0 seconds or
 - b. Osmolarity \geq 308 mosm/L in either eye or intraocular difference > 8 mosm/L or
 - Ocular surface staining (SICCA scale) > 5 corneal spots, > 9 conjunctival spots
 - d. Conjunctival-corneal epithelial damage (fluorescein, rose bengal, or lissamine green staining score >3 points).
- 3. Subtype Tests: severity according to the DEWS II Dx report;⁴ page 556
 - a. Aqueous tear deficiency: non-invasive meniscus height (TMH) ≤ 0.2 mm
 - b. Evaporative: only moderate to severe included:
 - Moderate: 1) orifice plugging, 2) lid margin vascularity, 3) gland secretion grade 8 – 12 (central 8 glands, 0 – 3 scale each),
 4) expressibility grade 2
 - Severe: 1) lid margin dropout or displacement, 2) gland secretion score ≥ 13, 3) expressibility grade of 3

The subjects will be recruited from among students, staff, faculty and patients from Ketchum Health, the clinical facility at Marshall B. Ketchum University. Additionally, the study will be advertised on social media to maximize the recruitment pool, such as Facebook, Instagram, and Twitter. Subjects will be sex-, and age-matched as they are enrolled since these parameters affect dry eye parameters such as marginal changes and meibomian gland secretion. ⁴⁴

Sample size estimation

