- 4. Corneal staining evaluation is quantified using the Ocular Staining Score (OSS) (only at screening and baseline).⁶¹ Punctate epithelial erosions (PEE) that stain with fluorescein are counted, and scored. If there are no PEE, the score is 0. If 1-5 PEE are seen, the corneal score is 1 (Appendix IV); 6-10 PEE are scored as 2; and >30 PEE are scored as 3. An additional point is added if 1) PEE occurred in the central 4mm diameter portion of the cornea; 2) one or more filaments are seen anywhere on the cornea; or 3) one or more patches of confluent staining, including linear stains, are found anywhere on the cornea. The total fluorescein score for the cornea (the PEE grade plus any extra points for modifiers) is noted in the central square of the SICCA ocular staining score form (Appendix IV). The maximum possible score for each cornea is 6.

Conjunctival Staining

9. A sterile lissamine green strip is wetted with a drop of sterile saline solution. The dye is applied on the superior bulbar conjunctiva on the right eye, followed by the

left eye. The subject is then moved back into the slit lamp headrest, and analysis is performed immediately after the dye was applied. The slit lamp biomicroscope is immediately utilized to visualize the bulbar conjunctiva with moderate high illumination of white light, wide beam (~14mm round), and 16x magnification. The subject is asked to look opposite to the side of the conjunctiva being visualized in order to reveal more of the conjunctiva clearly.

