10. Conjunctival staining evaluation is quantified using the OSS and NEI systems. In the OSS, grade 0 is defined as 0-9 dots of lissamine green staining of the interpalpebral bulbar conjunctiva (nasal and temporal conjunctivae graded separately); grade 1 is defined as the presence of 10 to 32 dots; grade 2 as 33 to 100; and grade 3 > 100 dots. Because of the difficulty of counting individual dots in a moving eye at the slit lamp, any area of confluent staining >=4 mm² is considered to be >100 dots. Nasal and temporal areas of the conjunctiva are graded separately with a maximum score of three for each area or a total maximum score of 6 for each eye. The total OSS for each eye is the summation of the fluorescein score for the cornea and the lissamine green scores for the nasal and temporal bulbar conjunctiva.⁶¹ The NEI scheme has an integer severity scale of 0 to 3 for each of six conjunctival sections (three sections each nasal and temporal sides) for a total corneal scale of 0-18.54-56 For both schemes, the scales are outlined with illustrated grading panels(Appendix III Case Report form). The scales assess the area, but not depth, of punctate staining, which increase on a log scale, with the highest number being the most staining and most severe. When the examiner grades the level of staining, the grading panels are readily visible and referenced during the evaluation.

Meibum Gland Excreta Grading

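### The written corneal rule of the Ocular Staining Score gives no grade to 11-30 erosions, leaving a one-point ambiguity in an exploratory measure

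*Combined protocol and SAP*

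**What the plan says.** Corneal Staining, item 4, sets out the corneal part of the OSS. It starts with "If there are no PEE, the score is 0", goes on with "If 1-5 PEE are seen, the corneal score is 1 (Appendix IV" in a sentence that cites the appendix form, and ends with "6-10 PEE are scored as 2; and >30 PEE are scored as 3". Up to three further points are added for central erosions, filaments and confluent patches. The result, "The total fluorescein score for the cornea (the PEE grade plus any extra points for modifiers" being its description, is entered on the SICCA form in Appendix IV, and "The maximum possible score for each cornea is 6". The same item limits corneal OSS to screening and baseline, as does Table 5.

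The Conjunctival Staining section adds the conjunctival grades to form the total OSS. There grade 0 covers 0 to 9 dots, and the rule continues: "grade 1 is defined as the presence of 10 to 32 dots; grade 2 as 33 to 100; and grade 3 > 100 dots".

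Under Evaluation criteria, Exploratory, the two items that use the score are "Comparison of National eye Institute (NEI) to Ocular Staining Score (OSS" (the line goes on to give efficiency as the aim) and "Repeatability of the above two staining schemes and meibomian gland secretion scores".

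**The concern.** A count-based grading rule should give every possible count exactly one grade. This one stops at 10 and resumes above 30. An examiner who counts 20 erosions finds no grade in the protocol text and, with nothing else to hand, would have to choose 2, choose 3 or leave the item blank.

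The gap matters most for repeatability. If two gradings of one eye resolve it differently, the disagreement looks like measurement error of the scale when its source is an incomplete rule. Corneal OSS is not scored after baseline, so later visits cannot replace a missing value. The trial recruits moderate to severe dry eye, and one route to diagnosis is more than 5 corneal spots, so counts just above the defined grade 2 band are plausible in this population.

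**Working it through.** **Inputs.** The corneal bands and modifiers are from Corneal Staining, item 4. The conjunctival bands are from Conjunctival Staining. The 0 to 12 total range is from Table 4 and Appendix IV.

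**Reproducing the stated maxima.** Highest erosion grade 3 + three modifiers = 6 per cornea, as stated. Adding nasal and temporal conjunctiva gives 6 + 3 + 3 = 12 per eye, as stated. The ends of the scale are therefore consistent; the fault lies inside it.

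**Mapping counts to grades.**

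| Corneal PEE count | Grade in the text |
|---|---|
| 0 | 0 |
| 1-5 | 1 |
| 6-10 | 2 |
| 11-30 | none |
| 31 or more | 3 |

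Ungraded values: 30 − 11 + 1 = 20. The conjunctival bands (0-9, 10-32, 33-100, above 100) leave no gap, which suggests that contiguous bands were intended for the cornea too.

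**Size of the ambiguity.** A count of 10 scores 2 and a count of 31 scores 3. If the grade does not fall as the count rises, every count from 11 to 30 must score 2 or 3.

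- Graded 2: corneal score 2 + (0 to 3 modifiers) = 2 to 5.
- Graded 3: corneal score 3 + (0 to 3 modifiers) = 3 to 6.

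For a given eye the two readings differ by one point on the 0-6 corneal scale and by one point on the 0-12 total. The maxima of 6 and 12 hold under both.

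**What uses the grade.**

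- The OSS side of the NEI-to-OSS comparison, and OSS repeatability, do.
- NEI corneal scoring does not: it grades each of five sectors 0 to 3 by area.
- Gland secretion scoring does not.
- The SICCA eligibility item (Subjects, criterion 2c) does not: it uses the raw count, and any count from 11 to 30 exceeds 5.
- The primary endpoints (fluorescein breakup time and secretion grade) do not, nor does the sample size, which rests on a breakup-time difference and SD of 2.5 seconds each.

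**Number of eyes.** The documents give no distribution of PEE counts. As an illustration only, 34 subjects have 68 eyes. If 10% to 50% fell in the gap (an assumption), that would be 0.10 × 68 = 6.8, about 7, to 0.50 × 68 = 34 eyes per visit.

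**The case against.** The strongest reply is that the working form may already be complete. Item 4 cites Appendix IV within the grading rule and has the score entered there, and the Conjunctival Staining section says that illustrated grading panels are in view during grading. Only the form's headings and its 0 to 12 range are legible in the text available, so its bands cannot be checked. This stands: it is not shown that examiners will have to guess. It does not remove the point, because a complete form would then disagree with the protocol text.

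Item 4 also has erosions counted before they are scored. If the counts are kept, grades can be assigned later. The documents do not show whether they are kept.

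The comparison of schemes is for efficiency, which the protocol does not define, and the statistical methods section gives no analysis for it. How far a one-point ambiguity would disturb that comparison is therefore not established.

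Three stronger readings are tempting, and the documents do not support them.

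- *The exploratory comparison and repeatability cannot be computed.* Only the corneal OSS component is undefined. NEI and gland secretion repeatability are intact.
- *Two thirds of cases are affected.* The ratio 20/30 = 67% is a share of the whole numbers from 1 to 30, not of eyes.
- *The gap changes which eye is analysed.* General Procedures picks the eye with the worse staining but names no scheme. Table 4 lists OSS and NEI totals together, but the dry eye classification uses NEI, the secondary endpoints name Oxford and NEI, and nothing indicates that OSS makes the choice.

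**Conclusion.** The rule is wrong as written, and the point is minor. Counts of 11 to 30 have no corneal OSS grade in the protocol text, so for those eyes the text does not define the corneal or total OSS at screening and baseline. The effect is one point (grade 2 or 3), confined to the OSS side of the comparison with NEI and to OSS repeatability. The conclusion assumes that grades do not fall as counts rise, and that nothing in the illegible part of Appendix IV overrides the text. The number of affected eyes is unknown.

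**What to change.** Make the corneal bands contiguous in Corneal Staining, item 4, and check them against the SICCA form in Appendix IV so that text and form agree. If the stated limits of 1-5 and >30 are right, grade 2 becomes 6-30 erosions, the natural correction. The text alone does not prove that 10 is the faulty number: keeping 6-10 and starting grade 3 above 10 would also close the gap, so the sponsor should confirm against the form. Recording the raw erosion count beside the grade would let any score already taken be regraded.

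The cost is one number in the protocol and a check of one form. Nothing changes in the sample size, the visit schedule or the primary analysis.

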In contradistinction, the studies by Worda et al⁸ and Connor et al.^{16-21,26,31} have examined topical eyelid androgen application with generally favorable effects on tear film parameters and also a good safety profile. However, the eyelid application studies were not consistent in the subject type (e.g., both males and females were not uniformly enrolled), the androgen status and serum levels were not assessed prior to, or following androgen application and the studies were only published as peer-reviewed abstracts and mostly were done in one laboratory. This prospective randomized, controlled double masked study aims to evaluate the efficacy and safety of topical transdermal application to the eyelids of low dosage androgen in a population of patients with evaporative dry eye associated with meibomian gland dystrophy and aqueous tear deficient dry eye.

Methods

Study objective

To evaluate the safety and efficacy of an FDA-approved androgen nasal supplement (Natesto, Acerus Pharmaceuticals Corporation, 4.5% gel concentration) in males and females with dry eye of either aqueous tear deficiency or evaporative subtype.

Clinical hypothesis

- Natesto applied to upper and lower eyelid skin is more effective than placebo as measured by fluorescein tear breakup time (TBUT) and mean scores for meibomian secretion quality at 4 weeks and overall ocular comfort at 8 weeks.
- Natesto has an acceptable safety profile in ocular structures and general systemic system.

Statistical Hypotheses:

H₀: There is no difference in change from baseline to week four for either fluorescein breakup time (TBUT) or meibomian secretion score (0 - 24 scale) between the test and placebo-treated sample.

 H_A : There is a difference in the change from baseline to week four for either fluorescein breakup time (TBUT) or meibomian secretion score (0 – 24 scale) between the test and placebo-treated sample

Overall study design

Structure

We propose a randomized controlled trial (RCT) of one month duration dosing BID with

an FDA-approved androgen nasal supplement (Natesto, Acerus Pharmaceuticals

Corporation, 4.5% gel concentration) in males and females with dry eye of either aqueous tear deficiency or evaporative subtype.

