The test formulation will be marketed Natesto gel, containing 5.5 mg testosterone per pump (17 β -Hydroxyandrost-4-en-3-one; inactive ingredients are castor oil, oleoyl polyoxylglycerides and colloidal silicone dioxide; Natesto package insert). The placebo is the exact same formulation without 17 β -Hydroxyandrost-4-en-3-one. The drug and placebo will be delivered to and dispensed by Caduceus Medical group in Yorba Linda for MBKU's study use.

Dosage regimen

One dose per eyelid of masked gel, which is one pump from the dispenser, represents 5.5 mg for each eyelid, will be applied on the surface of upper and lower eyelid skin each eye twice per day (separated by 8 hours) for a total daily dose of 22mg.

Duration

2-week screening period; 4-week masked treatment phase, 8-week washout phase.

Overall study duration 14 weeks

Visit schedule (see Table 4 and 5)

- Visit 1: Screening visit (Day -14)
- Visit 2: Baseline (Day 0) : the drug (placebo) is prescribed and dispensed.
 Instructions are given on how to properly apply the drug. Subjects are instructed to keep the container even if the drug is finished. All containers need to be checked in the following two visits (visit 3 & 4)
- Visit 2a: serum blood draw for baseline total testosterone level, hematocrit, lipid panel, PSA for men only at clinical laboratory

- Visit 3: Two-week visit: check the drug (placebo) to see if supplement needed.
 Empty containers need to be collected.
- Visit 4: Week 4: the drug (placebo) is discontinued. All dispensed containers need to be collected.
- Visit 4a: serum blood draw for treatment period total testosterone level at clinical laboratory (must be in AM, and must be within two hours of application)
- Visit 5: Week 8: 4-weeks washout phase follow up
- Visit 6: Week 12: 8-week washout phase follow up

Evaluation criteria

Efficacy measures

Primary

- Fluorescein tear breakup time (FTBUT)
- MGD secretion grade (0-24 scale)

Secondary:

- 1. Schein Questionnaire and Ocular Surface Disease Index (OSDI)
- Corneal and conjunctival staining as per the Oxford and National Eye Institute (NEI) schemes
- Tear Meniscus Height (TMH) utilizing Keratography 5M (K5M Oculus, Inc Arlington,WA)
- 4. Eyelid signs grading of orifice metaplasia, vascularity, plugged orifice, lid margin irregularity, ridging between orifices, and antero-posterior orifice displacement
- 5. Meiboscore utilizing K5M
- 6. Schirmer I test without anesthetic

Exploratory:

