Informed		v /			,	,, , ,, , ,, , ,, , ,, , ,, , ,, , , , , , , , , , , , , , , , , , , ,
Consent /	Χ					
HIPAA						
Medical/C	N/					
L History	Х	X				
Ophthalm						
oscopy		X		Х		х
exam						
Visual						
Acuity	Х	X	X	X	X	X
Hair						
evaluation		X		X		X
Blood						
Pressure		X		X		Х
Blood						
draw for						
sex		Х		X		
hormone						
Questionn						
aires:						
OSDI,	Х	Х	Х	x	x	Х
Schein,						
MGD-						
Specific						
Biomicros						
copy:						
general,	х	Х	х	x	x	х
and lid	~	X		~	^	~
signs (0 –						
5 scale)						
Tear	Х	Х	х			Х
osmolarity	~	~	~			
NIBUT						
(Keratogr	Х	Х	Х	x	x	Х
aph)						
Tear						
meniscus						
height	Х	Х	Х	x	х	Х
(Keratogr						
aph)						
TBUT,						
seconds						
(fluorescei	Х	Х	х	x	x	х
n; nearest						
1/10 th)						

 Table 5: Schedule of visits and procedures

$\begin{tabular}{ c c c c } \hline \hline Corneal \\ Staining^a: \\ Both OSS \\ (0-12) \\ and NEI \\ (1995) \\ scale (0- \\ 33) \\ \hline \end{tabular}$	OSS and NEI	OSS and NEI	NEI X	NEI x	NEI X	NEI X
Conjuncti val Staining [,]	х	х	х	x	х	х
Total Staining, for Severity Purposes:	Х	Х	Х	x	х	х
Meibomia n Gland Excreta Grading (0-24)	х	х	Х	x	х	х
Gland Imaging:	Х			x		х
Schirmer I sans anesthetic; 5 mins	Х	X	X	x	X	X
IOP Drug or Placebo Applicatio n		x Initiate Drug or Placebo Applicatio n		x Halt Drug or Placebo Applicatio n		X

Procedure I: Enrollment

- Informed consent and HIPAA documentation and California Research Subject's Bill of Rights. We will discuss the study with subjects and check verbally that they have understood important points, particularly potential risks.
- Comprehensive Ocular and Medical History

- The history questionnaire, which includes questions on contact lens use as well as complete medical and ocular history, will be administered by the examiner and used to further determine whether the subject met the inclusion and exclusion criteria.
- Verify compliance with guidelines for visit preparation
- Best Corrected Visual Acuity (BCVA) (OD/OS)
- BCVA must be 20/25 (0.1 log MAR) or better OD and OS
- LogMAR chart, calibrated at a testing distance of ten feet, and Snellen Equivalent will be recorded.
- If the subject was deemed eligible to participate in the study, they will be asked to participate in Procedure II.

Procedure II: Dry Eye Work-up

- Symptomatology questionnaires (Appendix II Symptoms questionnaires):
- Schein questionnaire;⁴⁷a score of \geq 7.5 out of 24 indicates dry eye.⁴⁸

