1. Procedure: Gland expression is assessed using a slit-lamp biomicroscope at medium (16x) magnification, moderate white light and a wide, 14 mm diffuse beam. A constant pressure device, the Meibomian Gland Evaluator (MGE) developed by Blackie and Korb in 2008⁵⁸ is utilized, allowing for standardized and consistent pressure. Prior to gland expression, a Q-tip wetted with non-preserved saline will be used to gently wipe the lid margin to remove any debris.⁵⁸ First, the subject is informed that they will feel a tickling sensation on the eyelid margin as it gets wiped with the Q-tip, and the pressure exerted by the MGE is demonstrated on the subject's hand. The subject is instructed to look up and away from the Q-tip or the MGE for the duration of the procedure. To clean the eyelid margin, the investigator gently pulled the skin down by placing the index finger over the edge of the orbital margin in order to prevent any accidental expression of the meibomian glands. Once the eyelid margin is revealed, it is gently wiped with a moistened Qtip. The investigator held the MGE 1-2 inches from the tip and applied it to the subject's lower eyelid at the base of the lash line to locally push the tarsal plate of the lower eyelid against the globe to express the meibomian glands. As the MGE is applied, it is angled down and the pressure was held for 10 - 15 seconds, watching for oil excretion from the glands to evaluate both the secretion quality and number of glands expressing oil. Expression proceeds targeting approximately 8 glands at the center of lower eyelid. Expression grade and secretion quality are graded individually. The procedure is repeated for each eye.

2. Grading Scales: Grading is based on the average appearance of the center lower eyelid region of a single eye. The Bron scale, initially proposed in 1991,⁶² is utilized for Meibomian secretion quality, which uses the color and viscosity of the excreta observed graded on a scale of 0 to 3, as described in Table 6.^{6,57}

11.

Grade	Meibum	Meibum Quality Description
	Quality	
Grade 0	Clear	Normal
Grade 1	Cloudy	Diffusely turbid fluid secretions
Grade 2	Granular	Usually turbid fluid secretions, but contains particulate matter. The color of these secretions varies from whitish to yellow.

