Grade 3	Inspissated	A semisolid plug or a substance of toothpaste- like consistency; may be extruded as a plug or curled thread. Expression is usually delayed or requires extra pressure. The material contains keratinized epithelial cells.

Table 6: "Bron Scale" Meibomian Gland Expression Grading^{6,57}

12.

Schirmer 1 Test

13. The Schirmer test without anesthetic is performed with the subject's eyes gently closed. The subject is told to look upward and blink normally while the strip is placed in the right eye then the left. The Schirmer strips are placed at the junction of the middle and lateral one-third of the lower eyelid. After five minutes the strips are removed, and the amount of wetting is recorded in millimeters. While in the subject's eye, the strip is monitored carefully; if after 2 minutes no wetting is

observed the strip is repositioned for the remainder of the five minutes, and the action is recorded. Due to the discomfort during the procedure, if a subject wets a minimum of 10mm of both strips in less than five minutes, the strips are removed. Care is taken to avoid contaminating the test strip with skin oil from the examiner.^{46,59}

Meibography with LipiView II (TearScience, Morrisville, North Carolina, USA)

- The LipiView II (Tear Science, Morrisville, North Carolina, USA) instrument is used to assess the area of Meibomian gland loss. Images of the subject's eyes are saved on a password protected LipiView instrument consistent with HIPAA. The images are transferred to a flash drive then to a secure research computer for analysis using Image J software for percent Meibomian glands remaining.

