Appendix III: Dry Eye Classification Criteria and Appendix V: Staging the Severity of MGD-Related Ocular Surface Disease

17. General statistical methods and types of analyses

- Comparisons, ANOVA, meibomian secretion scores, meibomian gland dropouts, OSDI
- The primary visit is week 4 and primary efficacy variables are the FTBUT and quality of meibomian secretions
- A two-sided test with p-value less than or equal to 0.05 will be considered as statistically significant.
- 18. Comparisons between pairs of treatment groups will be done with Cochran-Mantel Haenszel (CMH) tests, stratified by the ocular discomfort strata. Within Strata comparisons will be done with Wilcoxon rank-sum tests for both ordinal and continuous variables. For nominal variables, within strata comparisons will be done with Pearson's chi-square or Fisher's exact tests.
- 19. Exploratory pharmacokinetics data analysis
- Summary statistics of testosterone, dihydrosterosterone, and 3-alphaandrostanediol glucuronide serum concentrations will be calculated. The relationships between treatment time and gender will be examined.

Confidentiality

The identity of the subjects will be treated as confidential. The results of the study, including any other data, may be published for scientific purposes but will not reveal the name of the subject or include any identifiable references to the subject. Although

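### The grading procedure for the meibomian secretion score, a primary endpoint, contradicts the score's own 0-24 definition

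*Combined protocol and SAP*

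**What the plan says.** All references are to the combined protocol and SAP.

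**The score and its uses**
- Statistical Hypotheses tests the change from baseline to week 4 in the "meibomian secretion score (0 - 24 scale").
- Evaluation criteria lists "MGD secretion grade (0-24 scale") as primary. Section 17 (General statistical methods) says the "primary efficacy variables are the FTBUT and quality of meibomian secretions", with week 4 as the primary visit.
- Table 5 schedules "Gland Excreta Grading (0-24") at all six visits.
- Inclusion item 12 requires a score of 8 or more on 0-24.
- General Procedures uses the secretion grade as tie-breaker when the two eyes have equal staining scores.

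**How the score is built**
- Subjects, item 3 (Subtype Tests): "central 8 glands, 0 – 3 scale each", with 8-12 as moderate and 13 or more as severe.
- Table 4 also names the central 8 glands and a 0-3 scale, without saying that each gland is graded or that grades are summed.

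**How the examiner is told to grade**
- Meibum Gland Excreta Grading, item 1: "Expression proceeds targeting approximately 8 glands at the center of lower eyelid".
- Item 2: "Grading is based on the average appearance of the center lower eyelid region of a single eye", using the 0-3 Bron scale of Table 6.
- Case report form, section X: the visible field is one overall grade on the same 0-3 scale.

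**Device**
- Procedure II (Secretion Quality) and item 1 of the grading section specify the MGE so that pressure is standardised. In item 1 the Q-tip only wipes the lid margin.
- The Table 4 note and the heading of form section X allow either a Q-tip or the MGE.

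**The concern.** The only detailed instruction for a primary endpoint, together with the visible form field, describes a different quantity from the one in the hypotheses, the visit schedule and the entry criterion. An examiner who follows the grading section records one number from 0 to 3 per eye, while the analysis and item 12 expect a number from 0 to 24. Someone must bridge the two, and the plan does not say how. Different bridges can give different scores for the same lid. The same number bears on entry, on which eye is analysed when staining is tied, and on the week 4 comparison.

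The device wording raises a related issue. The endpoint is a change from baseline, and the protocol gives standardised pressure as its reason for using the MGE. Permitting a Q-tip removes that assurance.

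**Working it through.** **The plan's own figure.** The only sample size is for fluorescein tear breakup time (FTBUT): difference 2.5 s, SD 2.5 s, two-sided alpha 0.05, two-sample t test. With n = 17 per arm, the degrees of freedom are 2 x 17 - 2 = 32 and the noncentrality is 2.5 / (2.5 x sqrt(2/17)) = 2.915. Exact power from the noncentral t distribution is 0.807037, which is the Table 2 value. The secretion score plays no part in it, so N = 34 does not depend on this point.

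**Range under each text**

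| Source | Unit graded | Range | Can reach 8? |
|---|---|---|---|
| Subtype Tests | 8 glands, 0-3 each, summed | 0 to 8 x 3 = 24 (25 values) | Yes: mean gland grade 8/8 = 1.0 |
| Grading section, item 2 | One average grade per eye | 0 to 3 | No: 3 < 8 |
| Form section X, visible field | One overall grade per eye | 0 to 3 | No: 3 < 8 |

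On the single-grade reading, the 8-12 and 13-or-more bands are also out of reach. On the summed reading they correspond to mean gland grades of 1.0 to 1.5 (8/8 to 12/8) and at least 1.625 (13/8).

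**Does any wording reconcile them?** The grading section says that expression grade and secretion quality are graded individually. That separates two attributes; it does not separate one gland from another, and the next item specifies an average. Table 4 names 8 glands but gives neither a per-gland instruction nor a total. No text states a sum or a multiplier.

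**What summing leaves open.** Item 1 says approximately 8 glands, whereas a 0-24 sum of 0-3 grades needs exactly 8. Table 6 has four grades and none for a gland that yields nothing, although it says of grade 3 that "Expression is usually delayed or requires extra pressure". If such a gland could be scored anywhere from 0 to 3 (an assumed range), each one moves the sum by up to 3 points. This shows why a rule is needed; it does not estimate an effect in this trial.

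**The case against.** The best defence is that the score is defined. Subtype Tests gives 8 glands at 0-3 each, Table 4 repeats the central 8 glands, and the sample-size section says the 0-24 system is one recommended by the MGD workshop and DEWS II committees. A trained examiner would probably sum. If the average in the grading section meant the arithmetic mean over 8 glands (an assumption), multiplying by 8 would return the sum exactly. Non-expression has a place of its own, because expressibility is graded separately. Some form figures are not shown, so a per-gland grid cannot be ruled out. The two procedural sections both name the MGE, and no text plans a change of device between visits.

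Much of this stands. A reader might infer that the endpoint cannot be produced, or that nobody could enrol. The documents do not support that, because the 8-gland construction is visible and is the only one that yields 24. A reader might also infer that only the values 0, 8, 16 and 24 can occur, or that the maximum is 21 or 27. The first needs an integer grade and a multiplier of 8 that the plan never states. The second needs 7 or 9 glands, against the 8 named in Subtype Tests and Table 4.

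The defence does not remove the conflict. The grading section still tells the examiner to give one average grade. A grid on the form would not change that sentence, and the separate expressibility grade does not say what a non-expressing gland contributes to the quality sum.

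**Conclusion.** The point holds as an internal contradiction in how a primary endpoint is measured. Subtype Tests implies a 0-24 sum over 8 glands; the grading section and the visible form field prescribe one 0-3 grade, whose maximum of 3 is below the entry threshold of 8. No conversion is written. The Q-tip option is a smaller inconsistency with the protocol's own reason for using the MGE.

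This should be corrected, but it does not invalidate the design: the intended construction can be inferred and the FTBUT-based sample size stands. The contradiction between Subtype Tests and the grading section is certain from the text. What the form finally records is less certain, because some of its figures are not shown. The documents allow no estimate of how far scores would shift in practice.

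A reader might also see entry errors here, and the documents do not support that reading. Section 16 enrols severity levels 3 to 5, and level 3 in the severity staging table (Appendix V) has quality 4-7. Item 12 already requires 8 or more of every subject, so those scores are screened out. Item 12 does not contradict the objective of covering either subtype, because an aqueous-deficient subject can also score 8 or more. At most, these passages need reconciling.

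**What to change.** 1. Check first whether a form figure, not shown in the public text, already has a per-gland grid.
2. In Meibum Gland Excreta Grading and form section X, replace the average or overall grade with a 0-3 grade for each of exactly 8 central lower-lid glands, summed to 0-24 per eye, as Subtype Tests implies. Print the eight entries and the total on the form.
3. State in advance how a gland that expresses nothing enters the sum.
4. Specify the MGE for expression at every visit, and delete the Q-tip alternative from Table 4 and the heading of form section X.
5. Ask the sponsor to reconcile section 16 and the severity staging table with Subtype Tests and inclusion item 12. No view is taken on which entry rule is right.

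Cost: wording, and recording time if there is no grid. Grades would then rise from 2 to 16 per visit (8 glands x 2 eyes), or from 12 to 96 per subject over six visits, from the same examination. With a grid, nothing extra is recorded. The 17 per arm does not change.
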